## **11.6 STUDY SIZE**

Sample size calculation has been based on study's primary endpoint, which involves the determination of the proportion of study population with clinically meaningful improvement in the LCSS ASBI score over a 6-month treatment period.

Due to the lack of published data on the effect of afatinib on symptom burden using the LCSS, the worst case scenario has been taken into account, i.e., that the proportion of patients experiencing symptom improvement (*as defined in Section 11.1.3.1*) after 6 months of therapy will be approximately 0.50. Consequently, the assessment of 96 patients is required to estimate the aforementioned proportion with a margin of error not exceeding 0.10 which represents a scientifically acceptable level of precision of the estimate [95% CI: 0.40-0.60;  $\alpha$ : 0.05; Relative Standard Error (RSE): 10.21%]. This means that for any proportion between 0.05 and 0.95, the precision will range from 0.04 to 0.10 at a 95% confidence limit. The sample size determination has been performed using the statistical software package SAS v9.4 (SAS Institute, Cary, NC).

In order to control for an estimated 25% drop out/non-evaluable rate, 128 patients are finally required in order to ensure the aforementioned sample size for the final statistical analysis.

## **11.7 DATA MANAGEMENT**

The study data collection will be carried out through WBDC and paper-and-pencil self-administered PROs.

The WBDC application will be specifically designed for the needs of the study by the designated Clinical Research Organisation (CRO) and will adhere to all applicable data protection regulations and requirements with regard to electronic records. The patients will be identified by subject identification number, site number, and study identification number.

Data (including those recorded in the paper PROs) will be entered in the WBDC system by the study personnel at the Investigator's site, according to the Investigator Instructions Manual. Data entered in the WBDC system will be automatically saved to a central database and changes tracked to provide an audit trail. When data have been entered, reviewed and edited, the Investigator shall sign the e-CRF electronically as per the agreed project process and data will be locked to prevent further editing.

Query management will be performed through built-in query management functionality that will be incorporated into the WBDC.

Prior to the onset of data management activities, a detailed data management plan (DMP) will be issued describing the procedure to be followed for processing all collected study data in order to ensure they are valid, complete and accurate for the interim and final statistical analysis. In addition, aiming at ensuring the expected quality of data, a thorough data cleaning session will be applied twice during the conduct of the study for the purposes of the interim and final analysis, respectively. When all data have been properly validated and the quality control procedure has been completed, a declaration of database lock will take place so that it can be confirmed that all important actions have

been properly performed. In addition, prior to database lock and prior to the initiation of any statistical analysis activities a comprehensive statistical analysis plan (SAP) will be drafted. The SAP will also include information regarding the statistical software(s) to be used for the analysis of the study data and any data imputation methods that may be applied.

## **11.8 DATA ANALYSIS**

The study is not aimed to confirm or reject any pre-defined hypotheses; therefore statistical analyses will be of explorative and descriptive nature.

Continuous variables will be summarized with the use of descriptive statistical measures (mean value, standard deviation, median and extreme values) and categorical/distinct variables will be displayed as frequency tables (N, %). The normality of distribution of continuous variables will be examined using the Shapiro-Wilk test in order to determine whether or not to use parametric methods for the analysis of the sample data.

Differences between the mean values of continuous variables will be evaluated using the paired t-test or the non-parametric analogue (i.e., Wilcoxon signed rank test).

All statistical tests will be two-sided and will be performed at a 0.05 significance level. The exact p-values will be reported, even for non-significant results, rounded to three (3) decimals unless the p-value is less than 0.001 (in such case P<0.001 will be reported). No adjustment for multiplicity of testing will be performed.

A SAP comprising a comprehensive and detailed description of the statistical methodology applied for the purposes of the interim and final analysis along with imputation methods for missing data will be prepared prior to database lock.

Statistical analysis will be conducted using a validated statistical software package [e.g., Statistical Analysis System (SAS)].

### **11.8.1 Study populations**

In accordance to the non-interventional design of the study, all statistical analyses will be performed in the Full Analysis Set (FAS) comprised of all eligible subjects who have been enrolled into the study regardless of whether or not they have finally completed their projected participation in the study.

The analysis of the primary objective of the study will be performed in the Per Protocol Set (PPS) which will include all eligible study patients with available data pertaining to the study primary endpoint, i.e. 6-month symptom improvement rate as per LCSS ASBI score.

Subsets of patients with available data will also be created and analysed for the purposes of secondary endpoint analyses.

Patients erroneously enrolled in the study (i.e., not fulfilling the eligibility criteria) will be excluded from all analyses of this study and any deviations from the protocol will be reported in detail in the clinical study report (CSR).

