### **11.1.3 Study primary and secondary endpoints**

#### **11.1.3.1 Primary endpoint/outcome measure**

- 6-month symptom improvement rate using the LCSS ASBI, i.e., proportion of patients who will experience a minimum clinically important improvement in symptoms (*defined as a decrease in the ASBI from enrolment  $\geq$ 10 in two consecutive assessments*) over 6 months of treatment.

Note: A patient will be categorized as having:

- an **improved ASBI** if the mean of any two consecutive post-baseline ASBI assessments for that patient is at least 10 points below the patient's ASBI at enrolment;
- a **worsened ASBI** if the mean of any two consecutive post-baseline ASBI assessments for that patient is at least 10 points above the value at enrolment;
- a **stable ASBI** if the mean of any two consecutive post-baseline ASBI assessments for that patient is within 10 points of the value at enrolment.

[figure not shown]
A change of 10 points on a 0-100 scale is considered sufficient to indicate a clinically meaningful change [32, 33, 34]; this magnitude is about the same as the 0.5 standard deviation that has also reported as a universally acceptable minimum clinically important difference [35].

[figure not shown]

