## **11.4       VARIABLES**

### **11.4.1      Primary outcome variable**

- ASBI score of LCSS -defined as the mean of the score of the 6 major lung cancer symptoms, i.e. loss of appetite, fatigue, cough, dyspnea, pain, and hemoptysis- at enrollment and at the 2-month intervals until the study visit at 6 months.

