## Statistical Analysis Plan

**Figure 1: Synoptic Study Diagram**

A total of 128 patients are planned to be enrolled by seven (7) Oncology and Pulmonology hospital centres/clinics in Greece specialized in lung cancer.

The overall study duration period is expected to be 60 months, including a 48-month enrolment period and a minimum 12-month follow-up period. During the observation period, data will be collected at routine clinical visits at 2-month intervals for the first 12 months and at 6-month intervals thereafter until the end of study participation.

In the context of this study which is planned to have an overall duration of 60 months, each participant will be treated with afatinib and observed in the context of the study until the end of study participation defined as a maximum of 48 months after afatinib treatment initiation or until disease progression, death, withdrawal of consent, unacceptable toxicity, study completion or physician's decision whichever occurs earlier. The maximum 48-month length of participation in the study pertains to the patients enrolled during the first 12 months of recruitment, while the maximum observation period for the last patient enrolled is 12 months.

Being non-interventional and observational in nature, this study does not impose any diagnostic/therapeutic interventions or strict visit schedule. Patients will be treated as per the routine medical practice in terms of visit frequency, types of assessments performed and with

[figure not shown]

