### 3.5 Analysis sets

In accordance to the non-interventional design of the study, all statistical analyses will be performed in the Full Analysis Set (FAS) comprised of all eligible subjects who have been enrolled in the study, regardless of whether or not they have finally completed their projected participation in the study.

The analysis of the primary objective of the study will be performed in the Per Protocol Set (PPS) which will include all eligible study patients with available data pertaining to the study primary endpoint, i.e. 6-month symptom improvement rate as per the LCSS ASBI score. In case that the size of the PPS differs substantially (i.e.  $\geq 20\%$ ) from the size of the FAS, then descriptive statistics of demographic and baseline disease and clinical characteristics will also be presented in the PPS.

Subsets of FAS with available data will also be created and analysed for the purposes of secondary endpoint analyses. The safety analysis will also be applied in the FAS.

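### The primary 'Per Protocol Set' is an evaluable (complete-case) set; at the plan's figures the full-cohort improvement rate could lie anywhere from 37.5% to 62.5% against a reported 50%, and the visible text plans no unconditional full-cohort proportion

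*Protocol*

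**What the plan says.** **Analysis sets.** Protocol 11.8.1 gives a general rule: "all statistical analyses will be performed in the Full Analysis Set (FAS) comprised of all eligible subjects who have been enrolled into the study", whether or not they completed. Its next paragraph then says: "The analysis of the primary objective of the study will be performed in the Per Protocol Set (PPS) which will include all eligible" patients with data on the primary endpoint. SAP 3.5 repeats both statements. Ineligible patients belong to neither set: "Patients erroneously enrolled in the study (i.e., not fulfilling the eligibility criteria) will be excluded from all analyses of this study".

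**Data needed to classify a patient.** A patient is improved if "the mean of any two consecutive post-baseline ASBI assessments for that patient is at least 10 points below" the enrolment value (Protocol 11.1.3.1). The ASBI is taken "at enrollment and at the 2-month intervals until the study visit at 6 months" (Protocol 11.4.1). One missing item of the six voids an ASBI (SAP 3.7.2). Physicians check the forms and point out blanks, but patients may leave items unanswered (Protocol 11.5.1).

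**End of participation.** Observation runs to at most 48 months, or to "disease progression, death, withdrawal of consent, unacceptable toxicity, study completion or" the physician's decision (SAP 2.3). Data taken at premature withdrawal count if they fall within a predefined time point (SAP 3.3).

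**Target.** Protocol 11.6 bases the sample size on the "determination of the proportion of study population with clinically meaningful improvement".

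**Related provisions.** If more than 20% are non-evaluable, SAP 4.2 adds an analysis of patients with at least one post-baseline ASBI and refers to section 8.1.3 for details. SAP 3.5 adds PPS baseline tables if the PPS and FAS sizes differ by 20% or more. SAP 5.1 reports withdrawal reasons.

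**The concern.** Eligibility already defines the FAS, so the PPS is the FAS minus patients without endpoint data. The name suggests a set selected on compliance, which it is not.

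Some reasons for missing data may be related to the outcome. On the natural reading, a patient needs ASBI scores at months 2 and 4, or at months 4 and 6. The documents do not say whether months 2 and 6 count as consecutive when month 4 is missing. A patient who progresses, dies or stops for toxicity before the second score is therefore normally dropped rather than counted as not improved, unless a withdrawal assessment supplies that score.

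This proportion is the main result of an uncontrolled, descriptive study. If non-evaluable patients improve less often than evaluable ones, the reported rate is too high for the enrolled eligible cohort, and its confidence interval gives no sign of that.

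**Working it through.** **Inputs.** Improvement proportion 0.50, 96 evaluable, 25% drop-out/non-evaluable, 128 enrolled (Protocol 11.6, SAP 2.4); Wald 95% limits (Protocol 11.8.2). Assumptions: all 128 are eligible, and q is the improvement proportion among non-evaluable patients. The documents give no value for q, so its full range is shown.

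**1. The plan's own figures.** n = 1.96² × 0.50 × 0.50 / 0.10² = 96.04, taken as 96. Half-width at 96 = 1.96 × √(0.25/96) = 0.100, so the CI is 0.40 to 0.60. Relative standard error = √(0.25/96)/0.50 = 10.21%. Enrolment = 96/(1 − 0.25) = 128. All reproduce. The plan therefore expects 128 − 96 = 32 non-evaluable patients and 48 improved among the 96.

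**2. Full-cohort rate.** FAS rate = (48 + 32q)/128. Gap = 0.50 − FAS rate = 0.25 × (0.50 − q).

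| q | FAS rate | Evaluable rate minus FAS rate |
|---|---|---|
| 0 | 48/128 = 37.5% | +12.5 points |
| 0.10 | 40.0% | +10.0 |
| 0.25 | 43.75% | +6.3 |
| 0.50 | 50.0% | 0 |
| 0.75 | 56.25% | −6.3 |
| 1 | 80/128 = 62.5% | −12.5 |

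The Wald CI is 29.1-45.9% at the lower bound and 54.1-70.9% at the upper bound.

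**3. If some of the 32 were ineligible.** They would leave the FAS too, and the worst case shrinks. With 4 ineligible (assumption): 50% − 48/124 = 11.3 points. With 8: 50% − 48/120 = 10.0 points.

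**4. The SAP 4.2 trigger.** Taking 128 as the denominator, 26 non-evaluable patients (20.3%) trigger the extra analysis and 25 (19.5%) do not. If each patient is independently non-evaluable with probability 0.25, the chance of more than 25 among 128 is 0.91, so at the planned rate the extra analysis would probably run. At 25 of 128 it does not, and the gap is 0.195 × (0.50 − q): 9.8 points at q = 0, 4.9 at q = 0.25, and −9.8 at q = 1.

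**5. What the extra analysis leaves out.** By its stated definition it excludes patients with no post-baseline ASBI. The documents do not give their number, so the gap remaining after that analysis cannot be calculated.

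**The case against.** The strongest objection is that SAP section 8, including the 8.1.3 to which SAP 4.2 refers, is not in the supplied text. Protocol 11.2 and Table 2 are also absent. Further handling may be specified there and must not be called missing. This stands, and it makes the recommendation conditional. It does not affect the visible definition of the PPS or the two statements about analysis sets.

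Second, the 25% scenario is one in which the SAP 4.2 analysis would probably run. This also stands: the 12.5-point worst case describes the evaluable-set rate alone. But the extra analysis is conditional, and patients lost before any post-baseline score remain outside it.

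Third, withdrawal assessments within a time point count, and physicians check forms for blanks. Both reduce the loss; neither removes it.

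Fourth, it can be argued that the endpoint concerns patients over six months of treatment, that the sample size openly removes non-evaluable patients, and that the FAS and PPS sentences read as a rule followed by an exception. The last reading is fair, but the text should say so. The first two do not settle the target, because Protocol 11.6 refers to the study population.

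Fifth, the study is descriptive, and a reader could compute the lower bound from the PPS and FAS counts. That is true, but such a reader would have to know that the PPS is defined by data availability. The patient-years improvement rate and the mixed models, planned only if applicable (Protocol 11.8.3), estimate other quantities.

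**Conclusion.** The point holds as one of labelling and reporting. The primary set is an evaluable set, and the visible text plans no unconditional 6-month improvement proportion in the FAS. At the plan's figures a reported 50% is compatible with a FAS rate from 37.5% to 62.5%, a spread wider than the reported interval of 40-60%.

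A reader might infer that the primary result will be overstated, or overstated by 12.5 points. The documents do not support that. The bounds are symmetric, and the sign reverses once more than 50% of non-evaluable patients improve. Overstatement is plausible because participation ends at progression or death, but a toxicity stop does not show that lung-cancer symptoms failed to improve. Progression may be recorded by imaging or laboratory criteria (SAP 6.2), and missed visits or blank items may be unrelated to outcome.

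The figures assume 128 eligible patients, 25% non-evaluable and 50% improvement among the evaluable. This should be fixed, with medium confidence given the absent section 8.

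**What to change.** Unless SAP section 8 already provides it, before database lock:

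1. In SAP 3.5, call the set an evaluable set, state that it needs two consecutive post-baseline ASBI scores by month 6, say whether months 2 and 6 qualify when month 4 is missing, and describe it as the exception to the FAS rule. Record the change in SAP 3.8, which now reports none. Align Protocol 11.8.1 at the next amendment.
2. Whatever the non-evaluable rate, report beside the evaluable-set rate the 6-month improvement proportion in the FAS with non-evaluable patients counted as not improved, plus best- and worst-case bounds. State that this count is conservative.
3. Tabulate non-evaluable patients by reason: progression, death, toxicity, other withdrawal, missed visit, missing item.

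**Cost.** A re-signed SAP version (SAP 1.2), slightly more analysis and no new data. A protocol change needs approval at each participating hospital (Protocol 11.11.1.1), so it can wait for another amendment. The downside is a lower companion rate that some may take as the main result. Its narrower interval (half-width 0.084 against 0.100) comes from assigning unobserved outcomes and is not extra information.

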### **11.8.2 Analysis for the primary endpoint**

Pertaining to the primary endpoint the proportion of patients experiencing a minimum clinically important symptom improvement (*as defined in Section 11.1.3.1*) over a 6-month period of treatment will be calculated along with the respective 95% confidence interval; in addition the relevant proportions of patients whose symptom burden has remained stable and deteriorated will be calculated. The 95% confidence interval will be derived from Wald confidence limits for a binomial proportion.

In order to examine the impact of baseline characteristics including among others, gender, age, BMI, educational/marital/employment status, disease stage, histological subtype, sites of metastases, EGFR mutation subtype, smoking status and smoking history, ECOG PS, type of concomitant medications and comorbidities, as well as adherence to therapy at 6 months on the study primary endpoint, a binary logistic regression model will be applied.

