## 3 DATA ANALYSIS CONSIDERATIONS

### 3.1 General presentation of summaries and analyses

Statistical analysis and generation of tables and patient data listings will be performed using SAS® statistical analysis software (the most updated version at the time of analysis onset). Figures will be created by validated graph programs, such as SAS® and/or Microsoft Excel.

Summary statistics will consist of frequency tables ( $n_{pt}$ , %) for categorical variables. For continuous variables, descriptive statistics [number of patients with available observations ( $n_{pt}$ ), number of missing observations ( $n_{miss}$ ), mean, standard deviation (SD), median, 25th and 75th percentiles, minimum (min) and maximum (max)] will be tabulated.

The normality of distribution of continuous variables will be examined using the Shapiro-Wilk test. Concerning binomial proportions 95% CIs will be derived from Wald confidence limits for binomial proportions. In order to examine the differences in the values of continuous variables, the paired t-test or the Wilcoxon signed-rank test for two dependent samples will be used. The association between categorical variables will be assessed with the use of the McNemar's test for paired samples.

Potentially, linear mixed-effects models for repeated-measures will be fitted in order to describe the trend of continuous variables over time. The impact of patient characteristics on variables of interest will be evaluated with the use of logistic regression models for dichotomous outcome variables. Pertaining to data presentation, when reporting relative frequencies or other percent values the following rules will apply:

- ✓ For values where all patients fulfil a certain criterion, the percent value will be displayed as 100.0.

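### The Wald interval set for the primary improvement proportion, and for any other binomial interval, falls short of 95% coverage towards the ends of the 0.05 to 0.95 range over which the plan claims 95% precision

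*Protocol*

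**What the plan says.** Protocol 11.8.2 calculates the proportion of patients with improved ASBI over 6 months, with a 95% confidence interval, and fixes the method: "The 95% confidence interval will be derived from Wald confidence limits for a binomial proportion". It also has the stable and deteriorated proportions calculated, without explicitly attaching an interval to them.

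SAP 3.1 gives the general rule: "Concerning binomial proportions 95% CIs will be derived from Wald confidence limits for binomial proportions". The public text offers no score or exact alternative for proportions.

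Protocol 11.6, repeated in SAP 2.4, plans on a proportion that "after 6 months of therapy will be approximately 0.50" and concludes that "the assessment of 96 patients is required to estimate the aforementioned proportion with a margin of error not exceeding 0.10". It then extends the claim: "for any proportion between 0.05 and 0.95, the precision will range from 0.04 to 0.10 at a 95% confidence limit".

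**The concern.** The Wald interval takes its standard error from the observed proportion. When few patients have the outcome, or nearly all do, that standard error tends to be too small. The interval is also forced to be symmetric about the estimate. It can then exclude the true value much more often than 5% of the time.

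This matters because the plan does not confine its precision claim to a rate near one half. It names 0.05 and 0.95 as the ends of the range, and it chose 0.50 because no published LCSS data on afatinib existed, so 0.50 is not a forecast. The study tests no pre-defined hypothesis, so the estimate and its interval are the main output for the primary endpoint. If the observed rate were low or high, the interval would carry a 95% label that the method does not earn.

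**Working it through.** **Inputs.** Evaluable n = 96, planning proportion 0.50, margin 0.10, relative standard error 10.21%, and 25% drop-out giving 128 enrolled (Protocol 11.6, SAP 2.4). Two-sided 0.05 level, so z = 1.96 (Protocol 11.8). Wald limits (Protocol 11.8.2, SAP 3.1).

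**Step 1: reproduce the plan's figures.**
- n = z² p(1−p)/d² = 1.96² × 0.25/0.10² = 96.04, stated as 96.
- Standard error at 0.50 = √(0.25/96) = 0.05103. The half-width is 1.96 × 0.05103 = 0.100, and the relative standard error is 0.05103/0.50 = 10.21%.
- Enrolment = 96/0.75 = 128.
- Half-width at 0.05 = 1.96 × √(0.05 × 0.95/96) = 0.0436, stated as 0.04.

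All figures reproduce. The last line shows that the 0.04 in the precision sentence is itself a Wald half-width.

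**Step 2: the two intervals.** With x events and p̂ = x/n:
- Wald: p̂ ± z√(p̂(1−p̂)/n).
- Wilson: centre (p̂ + z²/2n)/(1 + z²/n), half-width z√(p̂(1−p̂)/n + z²/4n²)/(1 + z²/n).

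**Step 3: exact coverage.** For a true p, sum the binomial probabilities P(X = x) over every x from 0 to 96 whose interval contains p.

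At p = 0.05 the Wald interval contains the truth only for x = 3 to 10. It misses for x = 0, 1 or 2 (probability 0.1358, upper limit too low) and for x of 11 or more (probability 0.0086, lower limit too high). Coverage is 1 − 0.1358 − 0.0086 = 0.856.

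| True proportion, n = 96 | Wald | Wilson |
|---|---|---|
| 0.05 (and 0.95) | 85.6% | 94.2% |
| 0.10 (and 0.90) | 91.3% | 96.1% |
| 0.15 | 94.7% | 95.6% |
| 0.20 | 94.1% | 94.5% |
| 0.30 | 95.4% | 95.5% |
| 0.50 | 94.8% | 94.8% |
| Mean over 0.05 to 0.15 | 92.6% | 95.2% |
| Mean over 0.05 to 0.95 | 93.9% | 95.1% |

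The means are over an evenly spaced fine grid. If all 128 patients were evaluable, Wald coverage at 0.05 would still be only 88.2% (Wilson 96.2%).

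**Step 4: effect on a reported interval at n = 96.**

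| Events | Wald | Wilson | Half-widths (Wald, Wilson) |
|---|---|---|---|
| 5 | 0.008 to 0.096 | 0.022 to 0.116 | 0.044, 0.047 |
| 29 | 0.210 to 0.394 | 0.219 to 0.400 | 0.092, 0.090 |
| 48 | 0.400 to 0.600 | 0.402 to 0.598 | 0.100, 0.098 |

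At 5/96 the widths are close. The main difference is that Wilson moves the interval upwards.

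**The case against.** Several counter-arguments stand and limit the point.

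- **Which proportions are affected.** A reader might infer that every proportion in the report will carry a Wald interval, and that the worsened share will therefore be shown with limits that are too narrow. The documents do not support this. Protocol 11.8.2 attaches an interval to the improvement proportion only, and other proportions are set out as counts and percentages. SAP 3.1 fixes a method for whatever intervals are produced; it does not require one for each proportion. SAP section 8, which holds the efficacy analyses, is not in the public text, so intervals on the worsened or stable shares can be neither assumed nor ruled out.
- **Zero events and negative limits.** The collapse to zero width at 0/96, and the negative lower limits at 1 to 3 events of 96, are real properties of the method. They occur at observed proportions below the range the plan claims, and zero events is implausible for the primary rate: even at a true 0.05 its probability is 0.95^96 = 0.7%.
- **Worst point.** 85.6% is the minimum within 0.05 to 0.95. Wald coverage oscillates, reaching 94.4% at 0.065 and 94.5% at 0.08, where it is slightly above Wilson (94.1% and 94.3%). Wilson also dips, to about 92.7% at its lowest.
- **Half-width versus coverage.** The precision sentence can be read as a statement about half-width alone, and as such it reproduces. But it attaches a 95% level to that half-width, and the method does not deliver that level near the ends.
- **Consequences.** The analysis is exploratory and no decision rule hangs on the interval. At 29/96 or 48/96 no conclusion would change.

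**Conclusion.** The point holds as a modest but free improvement. With 96 evaluable patients the prescribed Wald limits are adequate near the planning value of 0.50. They fall short of the claimed 95% towards the ends of the plan's own range: 85.6% at 0.05, 91.3% at 0.10, and 92.6% on average over 0.05 to 0.15. At 0.05 the misses are mostly on one side, with the upper limit below the truth 13.6% of the time.

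The practical effect is small unless the observed proportion is below about 0.15 or above about 0.85. The figures of 96 and 128 are not in error. The coverage figures assume independent patients and a fixed denominator of 96. The documents support the point for the primary proportion and for any other single-proportion interval produced under SAP 3.1. Whether other such intervals are planned cannot be judged from the public text.

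**What to change.** - In SAP 3.1, replace Wald with Wilson score limits for the primary improvement proportion and for any other single-proportion confidence interval. Align Protocol 11.8.2.
- Restate the precision sentence in Protocol 11.6 and SAP 2.4 on the Wilson basis: a half-width of about 0.047 at 5/96 and 0.098 at 48/96. The 0.10 margin is kept with 96 evaluable patients. Clopper-Pearson limits would be a valid conservative choice, but at 48/96 they run from 0.396 to 0.604, a half-width of 0.104, just over the margin.
- Make the change before the results are seen.

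The cost is a programming option, a SAP version update and a wording change in the protocol. Protocol 11.11.1.1 requires hospital approval of amendments, so the protocol wording could wait for the next one. Until then, SAP 3.8, which now reports no change from the planned analysis, should record the difference.
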